APPENDIX 4. CONTRACEPTION GUIDELINES AND DEFINITION OF CHILDBEARING POTENTIAL

Contraception guidelines

The Clinical Trials Facilitation Group (CTFG) recommendations related to contraception and pregnancy testing in clinical trials include the use of highly effective forms of birth control. These methods include the following:

- Combined (estrogen and progestogen containing) hormonal contraception associated with the inhibition of ovulation
 - Oral, intravaginal or transdermal
- Progestogen-only hormonal contraception associated with the inhibition of ovulation
 - Oral, injectable, implantable
- An intrauterine device (IUD)
- Intrauterine hormone-releasing system (IUS)
- Bilateral tubal occlusion
- Vasectomized partner
- Sexual abstinence (defined as refraining from heterosexual intercourse during the entire period of exposure associated with the study treatment). Total sexual abstinence should only be used as a contraceptive method if it is in line with the patients' usual and preferred lifestyle. Periodic abstinence (eg, calendar, ovulation, symptothermal, post-ovulation methods), declaration of abstinence for the duration of exposure to study drug, and withdrawal are not acceptable methods of contraception.

Of note, barrier contraception (including male and female condoms with or without spermicide) is not considered a highly effective method of contraception and if used, this method must be used in combination with another acceptable method listed above.

Definition of childbearing potential

Childbearing potential is defined as being physiologically capable of becoming pregnant. No childbearing potential is defined as one or both of the following criteria:

- Surgically sterile (bilateral salpingectomy, bilateral oophorectomy, or hysterectomy)
- Post-menopausal, defined as
 - ≥ 55 years of age with no spontaneous menses for ≥ 12 months OR
 - < 55 years of age with no spontaneous menses for ≥ 12 months AND with a post-menopausal follicle-stimulating (FSH) concentration > 30 IU/mL

APPENDIX 5. NEW YORK HEART ASSOCIATION CLASSIFICATION

NYHA Class	Symptoms
I	Cardiac disease, but no symptoms and no limitation in ordinary physical activity, eg no shortness of breath when walking, climbing stairs etc.
II	Mild symptoms (mild shortness of breath and/or angina) and slight limitation during ordinary activity.
III	Marked limitation in activity due to symptoms, even during less-than-ordinary activity, eg walking short distances (20-100 m). Comfortable only at rest.
IV	Severe limitations. Experiences symptoms even while at rest. Mostly bedbound patients.

APPENDIX 6. PROHIBITED MEDICATIONS

Strong and Moderate CYP3A Inhibitors and Strong CYP3A Inducers

Strong CYP3A Inhibitors
Antibiotics: clarithromycin, telithromycin, troleandomycin
Antifungals: itraconazole, ketoconazole, posaconazole, voriconazole
Antivirals: boceprevir, telaprevir
Other: cobicistat, conivaptan, elvitegravir, mibefradil, nefazodone
Protease Inhibitors: indinavir, lopinavir, nelfinavir, ritonavir, saquinavir, tipranavir
Strong CYP3A Inducers
Avasimibe, carbamazepine, mitotane, phenobarbital, phenytoin, rifabutin, rifampin (rifampicin), St. John's wort (Hypericum perforatum)
Moderate CYP3A Inhibitors
Antibiotics: ciprofloxacin, erythromycin
Antifungals: fluconazole
Protease inhibitors: amprenavir, atazanavir, darunavir, fosamprenavir
Calciumchannel blockers: diltiazem, verapamil
Tyrosine kinase inhibitors (anticancer): imatinib
Food products: grapefruit juice (citrus paradisi fruit juice)
Herbal medications: Schisandra sphenanthera
Others: aprepitant, casopitant, cimetidine, cyclosporine, dronedarone, tofisopam

Data compiled from the FDA's "Guidance for Industry, Drug Interaction Studies;" <http://www.fda.gov/drugs/developmentapprovalprocess/developmentresources/druginteractionslabeling/ucm093664.htm> from the Indiana University School of Medicine's "Clinically Relevant" Table <http://medicine.iupui.edu/flockhart/table.htm>; from the University of Washington's Drug Interaction Database www.druginteractioninfo.org

APPENDIX 7. MEDICATIONS TO BE USED WITH CAUTION

Sensitive CYP2C9 Substrates or CYP2C9 Substrates with Narrow Therapeutic Index

- celecoxib¹
- Phenytoin²
- Warfarin²

- ¹ Sensitive substrates: Drugs that exhibit an AUC ratio (AUC_i/AUC) of 5-fold or more when coadministered with a known potent inhibitor.
- ² Substrates with narrow therapeutic index (NTI): Drugs whose exposure-response indicates that increases in their exposure levels by the concomitant use of potent inhibitors may lead to serious safety concerns (eg, Torsade de Pointes).

Strong CYP2C8 Inhibitors

- gemfibrozil

Data compiled from the FDA's "Guidance for Industry, Drug Interaction Studies;"
<http://www.fda.gov/drugs/developmentapprovalprocess/developmentresources/druginteractionslabeling/ucm093664.htm>
from the Indiana University School of Medicine's "Clinically Relevant" Table
<http://medicine.iupui.edu/flockhart/table.htm>; from the University of Washington's Drug Interaction Database
www.druginteractioninfo.org

C _{trough}	lowest concentration reached before the next dose administered
DCR	disease control rate
DLT	dose limiting toxicity
DOR	duration of response
ECG	Electrocardiogram
ECOG	Eastern Cooperative Oncology Group
eCRF	electronic case report form
GBM	glioblastoma
KM	Kaplan-Meier
MAD	maximum administered dose
MedDRA	Medical Dictionary for Regulatory Activities
MGMT	O ⁶ -methylguanine-DNA methyltransferase
MTD	maximum tolerated dose
NCI	National Cancer Institute
ORR	objective response rate
OS	overall survival
PD	progressive disease
PK	pharmacokinetic
PFS	progression-free survival
PR	partial response
PT	preferred term
RANO	Response Assessment in Neuro-Oncology
RT	radiotherapy
SAE	serious adverse event
SAP	Statistical Analysis Plan
SD	stable disease

SOC	system Organ Class
SPD	sum of the products of the perpendicular diameter
TEAE	treatment-emergent adverse event
TMZ	temozolomide
unmethylated GBM	GBM with unmethylated MGMT promoter

1 INTRODUCTION

The purpose of this statistical analysis plan (SAP) is to describe the procedures and the statistical methods that will be used to analyze the efficacy and safety endpoints and report results for BGB-290-104 protocol Version 2.0, dated July 23rd 2018: A Phase 1b/2 study to assess the safety, tolerability and efficacy of pamiparib in combination with radiation therapy (RT) and/or temozolomide (TMZ) in patients with first-line or recurrent/refractory glioblastoma (GBM). The focus of this SAP is for the planned primary, secondary efficacy and safety analyses specified in the study protocol.

2 STUDY OVERVIEW

This is an open-label, multicenter, multiple-dose, dose-escalation Phase 1b/2 study to determine the safety and pharmacokinetics (PK) of pamiparib in combination with radiation therapy and/or temozolomide with two initial arms (arms A and C) and a potential third arm (arm B). In arm A, pamiparib will be combined with RT in patients with first-line GBM with unmethylated MGMT promoter ('unmethylated GBM'). In arm B, depending on the safety of the arm A combination, pamiparib will be combined with both TMZ and RT in patients with first-line unmethylated GBM. In arm C, pamiparib will be combined with TMZ in patients with recurrent/refractory GBM with methylated or unmethylated MGMT promoter.

On completion of escalation cohorts, the study planned to enroll expansion cohorts for arm C and depending upon the emerging data, either arm A or arm B. Under protocol Version 2.0, dated July 23rd 2018, following completion of radiation treatment in Arms A and B, at the discretion of the investigator and after discussion with the medical monitor, patients may continue to receive pamiparib in combination with TMZ (maintenance).

Disease status will be assessed using Response Assessment in Neuro-Oncology (RANO) criteria. Patients will undergo tumor assessments at screening and then every 8 weeks, or as clinically indicated.

3 STUDY OBJECTIVES

3.1 PRIMARY OBJECTIVES

3.1.1. Phase 1b

Arm A (pamiparib + RT): Patients with first-line unmethylated GBM

- To assess safety and tolerability of pamiparib combined with RT
- To identify dose-limiting toxicities (DLTs) and determine the maximum tolerated dose (MTD) or maximum administered dose (MAD) and length of treatment for pamiparib combined with RT
- To select the recommended Phase 2 schedule for pamiparib combined with RT

Arm B (pamiparib + RT + TMZ): Patients with first-line unmethylated GBM

- To assess safety and tolerability of pamiparib combined with RT and TMZ
- To identify DLTs and determine the MTD or MAD for TMZ when combined with RT and the length of pamiparib treatment in combination with RT as determined in arm A
- To select the recommended phase 2 dose (RP2D) for TMZ when combined with RT and the length of pamiparib treatment as determined in arm A

Arm C (pamiparib + TMZ): Patient with recurrent/refractory GBM

- To assess safety and tolerability of pamiparib combined with TMZ
- To identify DLTs and determine the MTD or MAD for TMZ combined with pamiparib
- To select the RP2D for TMZ combined with pamiparib

3.1.2 Phase 2

Arm A, Expansion (pamiparib + RT): Patients with first-line unmethylated GBM

- To make a preliminary assessment of efficacy of pamiparib combined with RT followed by maintenance treatment of pamiparib + TMZ for those patients continuing onto maintenance treatment

Arm C, Expansion (pamiparib + TMZ): Patients with recurrent/refractory unmethylated or methylated GBM

- To make a preliminary assessment of efficacy of pamiparib combined with TMZ

3.2 SECONDARY OBJECTIVES

Phase 1b, all Arms

- Characterize the PK of pamiparib in combination with RT and/or TMZ
- To make a preliminary assessment of pamiparib efficacy in combination with RT and/or TMZ

Phase 2, Arm A and C

- To further characterize the efficacy, safety and tolerability of pamiparib in combination with RT and/or TMZ
- To further characterize the PK of pamiparib in combination with RT and/or TMZ

4 STUDY ENDPOINTS

4.1 PRIMARY ENDPOINTS

Phase 1b, all Arms

- Incidence and nature of DLTs

- Incidence, nature, and severity of AEs, graded according to the NCI-CTCAE, v4.03
- Number of cycles (arm C and maintenance phase for arm A&B) and the dose intensity of each component of the treatment regimens, and changes in vital signs and clinical laboratory test results during and following study treatment

Phase 2, Arm A (pamiparib + RT)

- Modified disease control rate (mDCR) as assessed using the Response Assessment in Neuro-Oncology (RANO) criteria

Phase 2, Arm C (pamiparib + TMZ)

- Overall response rate (ORR) as assessed using RANO criteria

4.2 SECONDARY ENDPOINTS**Phase 1b, all Arms**

- PK parameters of pamiparib: trough plasma concentration (C_{trough})
- Modified DCR (Arms A and B), DCR (Arm C), ORR and clinical benefit rate (CBR)
- Time-to-event endpoints: duration of response (DOR), progression-free survival (PFS) and overall survival (OS)

Phase 2, Arm A (pamiparib + RT)

- ORR and CBR as assessed using RANO
- Time-to-event endpoints: DOR, PFS and OS
- Incidence, nature, and severity of AEs, graded according to NCI-CTCAE, v4.03
- The dose intensity of each component of the treatment regimens, and changes in vital signs and clinical laboratory test results during and following study treatment
- PK parameters of pamiparib: C_{trough}

Phase 2, Arm C (pamiparib + TMZ)

- DCR and CBR as assessed using RANO criteria
- Time-to-event endpoints: DOR, PFS and OS
- Incidence, nature, and severity of AEs, graded according to NCI-CTCAE, v4.03
- Number of cycles and the dose intensity of each component of the treatment regimens, and changes in vital signs and clinical laboratory test results during and following study treatment
- PK parameters of pamiparib: C_{trough}

5 SAMPLE SIZE CONSIDERATIONS

Approximately 300 patients (60 in Phase 1b and 240 in Phase 2) were originally planned for enrollment. The actual sample size in Phase 1b depended on the number of Cohorts enrolled per arm and was 46 patients. The overall sample size was reduced during the study since the expansion cohorts were considered too large for this nonrandomized and nonregistrational study. The sample size in arm A expansion cohort is 40 and the sample size in arm C expansion cohort is 30. Overall the total number of patients enrolled in this study was 116.

Due to the reduction in sample size of the arm C expansion cohort, the analysis will not separate patients by MGMT status.

In Phase 2, the original sample size calculation was carried out using modified DCR in Arms A and B and ORR in each expansion cohort of arm C.

- 1) Assuming modified DCR of 60% in Arms A and B vs. 40% in historical control, the study is powered at ~82% to show 20% difference in modified DCR using a one-sided alpha of 0.025 when $n = 60$ per expansion cohort. Due to the reduction in actual sample size to 40 patients, assuming an observed modified DCR of 60%, the lower bound of the 80% exact confidence interval (CI) for the estimated modified DCR will exclude values less than 48%. The minimum observed modified DCR that has an 80% exact CI excluding 40% will be 53% (21 out of 40).
- 2) Assuming ORR of 25% in arm C vs. 10% in historical control, the study is powered at ~85% to show an 15% difference in ORR using a one-sided alpha of 0.025 when $n=60$ per expansion cohort. Due to the reduction in actual sample size to 30 patients, assuming an observed ORR of 25%, the lower bound of the 80% exact CI for the estimated ORR will exclude values less than 16%. The minimum observed ORR that has an 80% exact CI excluding 10% will be 20% (6 out of 30).

6 STATISTICAL METHODS

6.1 ANALYSIS POPULATIONS

Safety Analysis Set: includes all patients who received any dose of any of the study treatments (pamiparib, RT and/or TMZ). The Safety Analysis Set will be used for efficacy and safety analyses.

Efficacy Analysis Set: includes all patients in the Safety Analysis Set who:

Arms A & B: had a tumor assessment at baseline and at End of Treatment unless discontinued treatment or study early due to disease progression or death prior to tumor assessment.

Arm C: had measurable disease at baseline and at least one postbaseline tumor assessment unless discontinued treatment or study early due to disease progression or death prior to tumor assessment.

DLT-Evaluable Analysis Set: includes patients from escalation cohorts only in the Safety Analysis Set who received ≥ 42 Gy of RT (Arms A and B) and $\geq 70\%$ of scheduled pamiparib (Arms A, B and C) and TMZ (Arms B and C) during the DLT assessment window. All patients who had a DLT event will be considered DLT-evaluable regardless of study treatment intensity.

PK Analysis Set: includes all patients for whom valid pamiparib PK parameters can be estimated.

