4.2.3. Assessment of Dose-Limiting Toxicity

Dose-limiting toxicities will be assessed during the DLT assessment window starting with the first day of study treatments for all cohorts. The following assessments must be obtained at the end of the DLT assessment window: complete physical examination, vital signs and weight, Eastern Cooperative Oncology Group (ECOG) performance status, ECG, hematology, chemistry, coagulation, urinalysis, AEs, and concomitant medications.

For Arm A, the DLT assessment window will depend on the time period of pamiparib administration during RT and will consist of the time period of combination treatment plus 4 weeks after the last scheduled combination treatment, eg, 6 weeks for Cohort 1 of Arm A when pamiparib is given during the first 2 weeks of RT, and 10 weeks for Cohort 3 of Arm A when pamiparib is given during 6 weeks of RT.

For Arm B, the DLT assessment window will depend on the time period of combined administration of pamiparib and TMZ during RT and will otherwise follow Arm A rules, eg, if TMZ will be given only for the first 3 weeks of pamiparib and RT, then the DLT assessment window will be 7 weeks.

For Arm C, the DLT assessment window will encompass the first cycle of 28 days.

Patients who withdraw or are withdrawn from the study prior to completing the DLT assessment window for reasons other than a DLT will not be considered evaluable for DLT and will be replaced if needed to meet patient number requirement for dose escalation. Patients who do not experience a DLT and who do not receive ≥ 42 Gy of RT (Arms A and B) and $\geq 70\%$ of scheduled pamiparib (Arms A, B and C) and TMZ (Arms B and C) dosing during the DLT assessment window will not be considered evaluable for DLTs and will be replaced if needed to meet patient number requirement for DLT assessment.

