11.2.1. Analysis Set

- The Safety Analysis Set includes all patients who received any study treatment (pamiparib, RT, and/or TMZ). The Safety Analysis Set will be used for all efficacy and safety analyses.
- The Efficacy-evaluable Analysis Set includes patients in the Safety Analysis Set who had baseline and at least one post-baseline tumor assessment, unless discontinued treatment or study early due to clinical progression or death prior to tumor assessment.
- The DLT-evaluable Analysis Set includes patients who received ≥ 42 Gy of RT (Arms A and B) and $\geq 70\%$ of scheduled pamiparib (Arms A, B and C) and TMZ (Arms B and C) during the DLT assessment window with sufficient safety assessments. All patients who had a DLT event will be considered DLT-evaluable regardless of study treatment intensity.
- The PK Analysis Set includes all patients for whom valid pamiparib PK parameters can be estimated.

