Appendix Table 3: Schedule of Assessments for Arm C (Pamiparib and Temozolomide) (Continued)

Study Phase	Screening ^a	Treatment ^b								End of Treatment ^c	Safety Follow-up ^d	Long-Term Follow-up ^d
		Cycle 1				Cycle 2		Cycle ≥3				
		D1	D8	D15	D22	D1	D15	D1	D15			
Concomitant medication(s) ^p	X	X	X	X	X	X	X	X	X	X	X ^p	X (~q12w) ^p
Pharmacokinetics ^q		X		X								
Blood for biomarkers ^r	X	X		X				X		X		
Tumor tissue ^s	X											
Survival follow-up												X (~q12w)

7/-14 to -1, Day -7/-14 to Day -1 of screening; aPTT, activated partial thromboplastin time; CSF, cerebrospinal fluid; D, day; ECG, electrocardiogram; ECOG, Eastern Cooperative Oncology Group; INR, International Normalized Ratio; MRI, magnetic resonance imaging; q8w ±7d, every 8 weeks ± 7 days; ~q12w, approximately every 12 weeks

^a Screening must occur within 28 days of Day 1. Assessments obtained within 14 days of Day 1 (pregnancy and laboratory assessments: within 7 days) do not have to be repeated on Day 1. Some assessments have a narrower screening window as shown in the table. It is highly recommended that general screening assessments such as physical examination and laboratory assessments should be conducted first to rule out ineligibility based on those grounds before more involved and/or invasive procedures are carried out.

^b Cycle 1 encompasses the dose-limiting toxicity (DLT) assessment window, and assessments of Day 1 of Cycle 2 at the end of the DLT assessment window are required for a patient to be DLT-evaluable. Assessments shown for Cycle 3 apply to all subsequent cycles except for MRI that occurs every second cycle (every 8 weeks).

^c The end-of-treatment (EOT) visit will occur within 7 days after a patient discontinued study treatment for any of the reasons outlined in [Section 6.5.1](#). A visit should be scheduled as soon as possible, but the EOT visit may occur later after discussion with the medical monitor for specific circumstances, such as prolonged hospitalization. The visit at which MRI showed progressive disease (PD) may be used as the EOT visit provided that all required assessments were performed. MRI does not have to be repeated if it was performed within 14 days of the EOT visit or at a prior response evaluation that documented PD. ECG does not have to be repeated if it was performed within 14 days of the EOT visit.

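### SAP 6.1 defines the DLT-evaluable set by dose received alone and drops the protocol's follow-up conditions, so incompletely observed patients can count as DLT-free

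*SAP*

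**What the plan says.** SAP 6.1 describes the set as one that "includes patients from escalation cohorts only in the Safety Analysis Set who received" the two dose thresholds: at least 42 Gy of RT in Arms A and B, and at least 70% of scheduled pamiparib (all arms) and TMZ (Arms B and C). The definition then ends: "during the DLT assessment window. All patients who had a DLT event will be considered DLT-evaluable regardless of study treatment intensity". It says nothing about how long the patient was observed or which safety assessments were done.

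The protocol has the same thresholds but does not stop there.

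- Section 4.2.3 has a separate rule that a patient who leaves the study "prior to completing the DLT assessment window for reasons other than a DLT will not be considered evaluable for DLT". Such a patient is replaced if the cohort needs it.
- Section 4.2.3 also says: "The following assessments must be obtained at the end of the DLT assessment window".
- Section 11.2.1 qualifies the dose thresholds as applying "during the DLT assessment window with sufficient safety assessments".
- Appendix Table 3, footnote b, says for Arm C that "assessments of Day 1 of Cycle 2 at the end of the DLT assessment window are required for a patient to be DLT-evaluable".

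SAP section 8 lists the departures from the protocol's planned analysis. It declares a change of analysis set for the primary efficacy analysis but does not mention the DLT-evaluable set. SAP 6.5.2 uses this set for the Phase 1b DLT summary, taking events from the adverse event eCRF. SAP 4.1 names DLT incidence as a Phase 1b primary endpoint.

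**The concern.** Dose received does not stand in for time observed. In Arms A and B the DLT window runs four weeks beyond the last scheduled combination treatment, so both thresholds can be met well before it closes. A DLT-free patient who then leaves the study, or is no longer assessed, is non-evaluable under the protocol. Under SAP 6.1 the same patient enters the denominator as having had no DLT.

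The effect runs one way. A patient with a DLT is in the set whatever the exposure, so the extra patients let in by the looser definition can only be non-events. SAP 6.2.3 imputes no missing data unless otherwise specified, and DLTs come from reported AEs, so the unobserved part of the window is in effect read as event-free.

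At stake is whether a Phase 1b primary endpoint is reported on the population the protocol defined. Because the protocol replaces patients who leave early, a patient and the replacement could both sit in the SAP denominator. The reported denominators could then differ from those used for escalation.

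**Working it through.** **Reproducing the plan's window lengths.** Window = weeks of combination treatment + 4 weeks. For two, six and three weeks this gives 2 + 4 = 6, 6 + 4 = 10 and 3 + 4 = 7 weeks. These match protocol 4.2.3, which gives "6 weeks for Cohort 1 of Arm A when pamiparib is given during the first 2 weeks of RT, and 10 weeks for Cohort 3" (the latter also in Arm A), and 7 weeks in the Arm B example. The four-week cohort follows as 4 + 4 = 8 weeks. In days the windows are 42, 49, 56 and 70 for two, three, four and six weeks. Arm C has 28 days.

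**Inputs.** RT is given 5 days a week at 1.8 or 2 Gy (protocol 7.1.3). Pamiparib is given twice daily for the first 2, 4 or 6 weeks of RT in Arm A, and continuously in Arm C. TMZ in Arm C is given on Days 1 to 21 (protocol 4.2.1). I assume no interruptions.

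**Day on which 42 Gy is reached.**
- At 2 Gy: 42/2 = 21 fractions, Day 29.
- At 1.8 Gy: 42/1.8 = 23.3, so 24 fractions, Day 32 with a Monday or Tuesday start (Day 34 with a later start).

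**Day on which 70% of drug is reached.**
- Two weeks: 0.7 × 28 = 19.6, so 20 doses, Day 10.
- Three weeks (if pamiparib also runs three weeks): 0.7 × 42 = 29.4, so 30 doses, Day 15.
- Four weeks: 0.7 × 56 = 39.2, so 40 doses, Day 20.
- Six weeks: 0.7 × 84 = 58.8, so 59 doses, Day 30.
- Arm C: pamiparib 0.7 × 56 = 39.2, so 40 doses, Day 20; TMZ 0.7 × 21 = 14.7, so 15 doses, Day 15.

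**Minimum share of the window that satisfies SAP 6.1** = later of the threshold days ÷ window length.

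| Regimen | Earliest qualifying day | Window (days) | Share |
|---|---|---|---|
| Six weeks concurrent | 30 (2 Gy) or 32 (1.8 Gy) | 70 | 42.9% or 45.7% |
| Four weeks | 29 or 32 | 56 | 51.8% or 57.1% |
| Three weeks (Arm B example) | 29 or 32 | 49 | 59.2% or 65.3% |
| Two weeks | 29 or 32 | 42 | 69.0% or 76.2% |
| Arm C | 20 | 28 | 71.4% |

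A later-week start at 1.8 Gy raises the six-week figure to 34/70 = 48.6%.

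**Allowing for AE collection after treatment stops.** Protocol 10.3.1 collects AEs until 30 days after the last study treatment or until new anticancer therapy, whichever is first. A patient who stops all treatment on Day 29–32 but stays in the study is covered to Day 59–62. That exceeds the 42-, 49- and 56-day windows. In the six-week cohort coverage runs to Day 60–62 of 70, or 85.7–88.6%. In Arm C, 20 + 30 = Day 50, beyond the 28-day window. The shares in the table therefore apply only to patients who leave the study, start new anticancer therapy or stop being assessed at that point.

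**Size of the dilution, for illustration.** One added non-event moves 1/6 (16.7%) to 1/7 (14.3%), or 2/6 (33.3%) to 2/7 (28.6%).

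**The case against.** The best defence is that little follows from the difference. The SAP summary is descriptive and carries no decision threshold. SAP section 5 reports Phase 1b enrolment as finished, at 46 patients. The documents do not say that any patient is affected, and the number could be zero. The protocol's own set definition in 11.2.1 contains no completed-window rule; that rule stands in 4.2.3. At the level of the set definition the SAP lost only the phrase on safety assessments, which the protocol does not define. All of this is true and limits the size of the point. It does not remove it: someone programming SAP 6.1 as written would include patients whom 4.2.3 makes non-evaluable.

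Four stronger readings are tempting, and the documents do not support them.

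- *Progression makes a patient non-evaluable under the protocol.* The 4.2.3 rule concerns leaving the study. Progression is a reason to stop treatment (6.5.1) and is not among the reasons for leaving the study (6.7). Section 7.1.5.1 keeps patients who stop treatment under follow-up.
- *Patients in general may be observed for under half the window.* That floor belongs only to six-week concurrent regimens, and only to patients who drop out of observation as described above.
- *The change could reverse an MTD finding, for example 2/6 becoming 2/7 against the one-third limit.* Escalation is decided during the study under protocol 4.2.2 and 4.2.3, not from the SAP table.
- *A missed end-of-window assessment always makes a patient non-evaluable.* Only the Arm C schedule says so. For Arms A and B the protocol requires those assessments but does not tie evaluability to them explicitly.

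**Conclusion.** The discrepancy is real and undeclared. SAP 6.1 keeps the dose thresholds but omits the protocol's conditions on remaining in the study through the window and on sufficient safety assessments. Followed as written, it can only add incompletely observed non-events, so any bias in the reported DLT incidence is downward. The effect is confined to the reported DLT rates and denominators. Its actual size depends on how many DLT-free patients met the thresholds and then failed the protocol's conditions, which the documents do not give. The minimum observed shares assume uninterrupted dosing, five fractions a week and, at 1.8 Gy, a Monday or Tuesday start. With cohorts of about six, even one such patient shifts the rate by roughly 2 to 5 percentage points, so the definition should be corrected before the DLT table is produced.

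**What to change.** In SAP 6.1, state that a patient without a DLT is DLT-evaluable only if three things hold: the dose thresholds were met, the patient did not leave the study before the DLT window ended, and safety assessments were sufficient. For Arm C the last condition means that the Cycle 2 Day 1 assessments were done. For Arms A and B, say in the SAP what counts as sufficient, because the protocol leaves it open. Keep the rule that every patient with a DLT is included.

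Add a listing of patients who met the dose thresholds but fail either of the other conditions, with the last day observed. If the simpler definition was intended, declare and justify it in SAP section 8.

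The cost is a short addition to the definition and one listing. A few patients may leave the denominator, and the DLT rate may then look slightly less favourable.
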